- If a participant is confirmed to be pregnant and plans to continue the pregnancy, the following will be performed: (1) Fetal ultrasound to confirm gestational age and developmental status of the pregnancy; (2) Syphilis test result and history of treatment will be collected from medical records if previously done and documented; otherwise, the participant will be referred for testing and potential treatment per local standard of care and the results will be collected from the subsequent medical records. Participants will also receive HIV testing and counseling as clinically indicated.
- Any participant with a new HIV diagnosis will be offered counseling, as clinically indicated. They will also be referred for care and treatment according to local guidelines. Viral load and CD4+ T cell count must be obtained on study.
- In case of a change in antiretroviral (ARV) medication (for PLWH participants), blood will be collected for viral load and CD4+ T cell count approximately 4 to 6 weeks since the change in medication.

Following completion of all procedures in the preceding list, and if results indicate that vaccination may proceed, vaccination dose is prepared and administered (see Section 8.4, Appendix H and Appendix I).

Immediately following vaccination, the participant remains in the clinic for observation for 15 minutes or more in accordance with current applicable guidance (eg, local guidance). After the observation period, participants will have a postvaccination assessment prior to clinic discharge, including assessment of:

- The injection site, (see Section 9.8.2 and
- Systemic symptoms (see Section 9.8.1).

See CoVPN 3008 (Ubuntu) SSP for details.

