## 9.4 Follow-up procedures

The following procedures are performed during follow-up per the schedules in [Appendix H](#) and [Appendix I](#):

- At all follow-up visits: symptom-directed physical examination if needed
- At the last clinic visit: abbreviated physical examination
- Assessment of targeted concomitant medications
- Blood collection and nasal swabs (as described in [Appendix B](#), [Appendix C](#), [Appendix D](#), [Appendix E](#), [Appendix F](#), [Appendix G](#), [Appendix H](#), [Appendix I](#), and [Appendix J](#)).
- Participants will be instructed to contact the clinic if they have any AEs to report. The clinic will contact the participant every 2 weeks, as described in Section 9.5.
- Urine pregnancy test for a participant who reports a new pregnancy and/or as clinically indicated
- If a participant is confirmed to be pregnant and plans to continue the pregnancy, the following will be performed: (1) Fetal ultrasound to confirm gestational age and developmental status of the pregnancy; (2) Syphilis test result and history of treatment will be collected from medical records if previously done and documented; otherwise, the participant will be referred for testing and potential treatment per local standard of care and the results will be collected from the subsequent medical records. Participants will also receive HIV testing and counseling as clinically indicated.
- Any participant with a new HIV diagnosis will be offered counseling, as clinically indicated. They will also be referred for care and treatment according to local guidelines. Viral load and CD4+ T-cell count must be obtained on study.

- In case of a change in ARV medication (for PLWH participants), blood will be collected for viral load and CD4+ T-cell count approximately 4 to 6 weeks after the change in medication. For participants being exited less than 4 weeks after a change in ART, the site may choose to follow up these individuals after exit.
- All pregnancies should be monitored to record the outcome of the pregnancy (eg viability, congenital malformations at birth) (see Section 9.12 and CoVPN 3008 (Ubuntu) SSP for details).

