## Appendix C Laboratory procedures table for Groups 2 and 4 (SARS-CoV-2 seropositive participants, main study)

Procedure	Ship to 	Assay	Location 	Tube 	Tube size  (vol. capacity) 	Vac 1	Vac 2
BLOOD COLLECTION							
Screening/Diagnostic							
HIV test 	Local Lab	EDTA	5mL	5	—	—	—
HIV Viral Load 	Local Lab	EDTA	5mL	5 	—	—	—
CD4+ T Cell Count 	Local Lab	EDTA	5mL	5 	—	—	—
SARS-CoV-2 POC Serology	Local Lab	EDTA	5mL	5	—	—	—
SARS-CoV-2 Serology	BARC	HVTN Labs	SST	5mL	—	5	—
Immunogenicity assays							
Humoral assays	BARC	HVTN Labs	SST	8.5mL	—	8.5	8.5
Gene Expression	BARC	HVTN Labs	Tempus	3mL	—	6	6
Visit total					20.0	29.5	19.5
56-Day total					20.0	49.5	69.0
NASAL SWAB SAMPLE COLLECTION							
SARS-CoV-2 PCR	Local Lab	Local Lab	—	—	X	X	X
SARS-CoV-2 Viral Sequencing 	BARC	HVTN Labs	—	X 	X 	X 	X 
URINE COLLECTION							
Pregnancy Test 	Local Lab	Local Lab	X	—	—	—	—

Greyed out visit (4) does not apply to this group.

 BARC = Bio Analytical Research Corporation South Africa (Pty) Ltd (Johannesburg, South Africa)

 HVTN Laboratories include: Bio Analytical Research Corporation South Africa (Pty) Ltd (BARC) (Johannesburg, South Africa); Duke University Medical Center (Durham, North Carolina, USA); KwaZulu-Natal Research and Innovation Sequencing Platform (KRISP, Durban, South Africa)

 Screening may occur over the course of several contacts/visits up to and including Day 1 prior to study product administration.

 Local labs may assign appropriate alternative specimen type, tube and volume for locally performed tests.

 HIV diagnostic test will be performed for all participants at screening and as clinically indicated.

 HIV Viral Load and CD4+ T Cell Count will be performed at screening or at any visit for participants with newly diagnosed HIV infection, at enrollment for known PLWH, approximately 4-6 weeks after any change in antiretroviral therapy (other than just dosage) for PLWH, at visit 5 for PLWH, and as clinically indicated (see Sections 9.2, 9.3, 9.4 and 9.9). HIV Viral Load and CD4+ T Cell Count do not need to be recollected if they were collected and the results available within the past 14 days.

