Calendar-time-based Cox proportional hazards models will be employed to estimate the hazard ratio (HR) between the bivalent vs. monovalent randomized arms. The model will be stratified by the 4 study groups and region (RSA vs. other), thus allowing for a different baseline hazard for each of the $4 \times 2 = 8$ strata. Since the comparison is between randomized groups, the main analysis will only adjust for a small number of covariates that are deemed important or known to be associated with COVID-19 risk to increase efficiency in statistical inference. In particular, sex-assigned-at-birth (Female vs. Male) and baseline history of TB (yes vs. no) were found associated with CDC endpoints in Part A analyses, and having had a recent infection is expected to be associated with COVID-19 risk. Therefore, sex-assigned-at-birth, history of TB at Month 6, and recent SARS-CoV-2 infection status at Month 6 (see definition in Section 5) will be adjusted for in all primary and secondary analyses comparing randomized bivalent vs. monovalent boost arms. These analyses will also be repeated within people who live with HIV (PLWH) and HIV-negative participants, separately. For analyses among PLWH, CD4 counts (\leq vs. > 500 cells/mm 3 at Month 6) and HIV viral load (detectable vs. not detectable at Month 6) will be further adjusted for in

addition to sex assigned at birth, history of TB and recent infection status. For analyses among HIV-negative participants, a subset of the covariates maybe considered to avoid data sparsity, with recent SARS-CoV-2 status as the leading covariate to consider. Specifically, for Cox regression among HIV-negative participants (PLWoH), we will not adjust for TB status due to data sparsity.

We also make comparisons of covariate-adjusted cumulative incidence curves for each comparison arm. We provide a full description of the covariate-adjustment strategies in Section 11.3.

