A small number (about 5%) of PLWH participants are missing CD4 cell count and/or HIV-1 viral load at enrollment or at Month 6. In order to adjust for CD4 cell count and HIV VL in various analyses and retain these participants, hard-imputation is used to assign a fixed CD4 cell count value and VL value for each of the participants with missing data. Specifically, for baseline values, within each study group (Group 1 or 2), HIV anti-retroviral therapy (ART) status (Yes, No or Missing) and Sex (Female or Male), missing baseline CD4 cell count is imputed to be the median CD4 count of those with observed baseline data. The same imputation is done for missing baseline VL. For Month 6 values, missing data will be imputed as the baseline observed or imputed value for CD4 cell count and VL. Missing data of history of TB at Month 6 is defined as negative.

References

Grambsch, P. M. and Therneau, T. M. (1994), “Proportional hazards tests and diagnostics based on weighted residuals,” *Biometrika*, 81, 515–526.

Approved

Signature Page for SCHARP-TMF-118029 v2.0

Reason for signing: Approved	Name: [name] Role: I am an author of the document. Date of signature: 01-Apr-2024 19:29:49 GMT+0000
Reason for signing: Approved	Name: [name] Role: I am an author of the document. Date of signature: 01-Apr-2024 19:56:27 GMT+0000
Reason for signing: Approved	Name: [name] Role: I reviewed and approved the document and am signing in lieu of or on behalf of another individual. Date of signature: 01-Apr-2024 21:23:53 GMT+0000
Reason for signing: Approved	Name: [name] Role: I am an author of the document. Date of signature: 02-Apr-2024 00:55:44 GMT+0000

Signature Page for SCHARP-TMF-118029 v2.0

Approved

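### SAP Section 13 fills a missing Month 6 CD4 count or viral load with the enrolment value even when a newer on-study result exists; the effect is small and the correction is nearly free.

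*Protocol*

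**What the plan says.** **Collection.** Protocol Appendix C, footnote 6, schedules viral load and CD4 count at screening or enrolment and then "approximately 4-6 weeks after any change in antiretroviral therapy (other than just dosage) for PLWH, at visit 5 for PLWH, and as clinically indicated". Appendices D, E and F carry the same timing. Protocol Section 9.4 says that after a change of antiretroviral medication "blood will be collected for viral load and CD4+ T-cell count approximately 4 to 6 weeks after the change in medication", and Section 9.3 has a matching instruction for vaccination visits. Visit 5 is the Month 6 vaccination visit. The appendix footnotes waive a new draw where results from the past 14 days are available.

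**Use.** SAP 7.1 says that in PLWH analyses CD4 count (cut at 500 cells/mm³) and "HIV viral load (detectable vs. not detectable at Month 6) will be further adjusted for". SAP 11.4.2 carries both into the Cox models for secondary analyses III to V. SAP 10.3 says their coefficients will be reported if of interest.

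**Missing values.** SAP Section 13 states: "A small number (about 5%) of PLWH participants are missing CD4 cell count and/or HIV-1 viral load at enrollment or at Month 6". Within study group, antiretroviral status and sex, "missing baseline CD4 cell count is imputed to be the median CD4 count of those with observed baseline data", and viral load is treated the same way. It then says: "For Month 6 values, missing data will be imputed as the baseline observed or imputed value for CD4 cell count and VL". No result measured between enrolment and Month 6 is mentioned.

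**The concern.** The covariate is meant to describe HIV status at Month 6. When that value is missing, the SAP goes back to Day 1, or to a group median, even if the participant has a later measurement. The later measurements are not a random sample. They arise mainly because antiretroviral therapy changed, which is when viral load and CD4 count are most likely to move. Both covariates are dichotomised, so a result that has crossed its threshold since enrolment is fully misclassified rather than slightly wrong.

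At stake are the quality of the adjustment in the PLWH Cox models and the meaning of the reported CD4 and viral-load coefficients. Protocol Section 2.1 links low CD4 count and HIV viraemia to persistent or recurrent infection, so readers may take an interest in those coefficients.

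**Working it through.** **1. The plan's own figure.** The only stated figure on this point is the 5% missing. It cannot be reproduced, because the documents give no counts. It covers CD4 and/or viral load, at enrolment or Month 6, so it is an upper bound on missing Month 6 values.

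**2. Which results can be newer than enrolment?**
- *Antiretroviral change other than dosage alone* (Protocol 9.3, 9.4; Appendices C to F): yes, if the change is early enough. With the dose on Day 169, a sample 4 to 6 weeks after the change precedes it only if the change came by about Day 127 (169 − 42) to Day 141 (169 − 28). Appendix G omits this trigger, but Sections 9.3 and 9.4 cover all PLWH.
- *As clinically indicated*: yes.
- *COVID-19 schedule* (Appendix J, Day 3): yes, but drawn during acute illness.
- *New HIV diagnosis*: in effect no. SAP Section 2 fixes study groups by baseline HIV serostatus, so someone first diagnosed after enrolment is in Group 3 or 4. The SAP Section 13 imputation works within Groups 1 and 2.

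**3. How many people?** Inputs: about 4,000 given their Month 6 dose under the randomisation (Protocol 6.3.1); about 80% PLWH (Protocol 2.3, assumed to hold in this cohort); 5% missing (SAP Section 13).
- PLWH: 4,000 × 0.80 = 3,200.
- Upper bound with a missing value: 3,200 × 0.05 = 160.
- With a newer result on file: 160 × *f*, where *f* is not given and is an assumption.

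| *f* | People | Share of 3,200 |
|---|---|---|
| 1% | 1.6 (about 2) | 0.05% |
| 5% | 8 | 0.25% |
| 10% | 16 | 0.5% |
| 20% | 32 | 1.0% |
| 50% | 80 | 2.5% |

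Only those whose newer result falls on the other side of a threshold would be coded differently, so the number recoded is smaller still.

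The full Month 6 cohort used in exploratory II is larger. A loose ceiling from all 14,237 enrolled is 14,237 × 0.80 × 0.05 = about 569, and 1% to 50% of that is about 6 to 285.

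**4. Which analyses use the value?**
- All-participant primary Cox models (SAP 11.4.1): no CD4 or viral load.
- Cumulative-incidence models (SAP 11.3.1): recent infection status and study group only.
- Severe COVID-19: SAP 7.1, 11.3 and 11.4.1 rule out covariate adjustment.
- Secondary III to V, COVID-19 Cox models in PLWH: yes.
- Exploratory II: unclear. SAP 8.2.1 names baseline CD4 count and viral load for this cohort; SAP 11.4.3 points to the secondary III strategy, which uses Month 6.
- Exploratory VI and VII: these take the Part A covariates at Month 6 where applicable. Whether they include CD4 or viral load depends on the pre-Month 6 SAP, which is not among the documents.

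**5. Power.** Recomputing the post-Month 6 rows of Protocol Table 6-2 (two-sided exact binomial at 0.05, event share RR/(1 + RR)) gives 54.1, 92.9, 87.4, 98.7, 78.1 and 96.2%, against 54, 93, 87, 99, 78 and 96% stated. The inputs are events, relative risk and alpha, so the imputation rule cannot move them.

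**The case against.** The other side has a good deal that stands.

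- *Everyone whose therapy changed gets an outdated value.* A reader might infer this, but all PLWH have viral load and CD4 count scheduled at visit 5. Someone who changed therapy normally has a true Month 6 result, and only a missing one triggers the rule.
- *The randomised comparison is biased.* The documents do not support this. The substituted values predate the Month 6 dose, so coding errors do not depend on arm. They cost a little precision in secondary III to V.
- *Exploratory II is left confounded.* This is possible but not established. If SAP 8.2.1 governs, the Month 6 rule never enters that analysis.
- *Treated participants have a suppressed result on file but are coded detectable.* Nothing in the documents shows suppression at 4 to 6 weeks; this is only a possible case.
- *Results under 14 days old are discarded at visit 5.* The SAP does not say so. It simply does not say whether such a result counts as the Month 6 value.
- *Carrying baseline forward is simple, prespecified and the same for everyone, whereas interim results are irregular and selective.* This is fair, and it is a reason to keep acute-illness draws out of the main rule. It does not justify preferring an older measurement, or a group median, to a newer one from the same person when the target is status at Month 6.

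**Conclusion.** The point holds in a narrow form. SAP Section 13 passes over newer measured results that the protocol provides for, in favour of the enrolment value or a median. It affects only PLWH with a missing visit 5 result: at most about 160 of 3,200 in the randomised cohort, of whom about 2 to 80 would have a newer result if the unknown share lies between 1% and 50%. These figures rest on the 80% PLWH share holding at Month 6 and on the pooled 5% as a ceiling.

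The consequences are slightly weaker adjustment in the COVID-19 Cox models of secondary III to V and some distortion of the CD4 and viral-load coefficients. Exploratory II is affected only on one of two conflicting readings. The effect on the randomised hazard ratio is negligible, and no primary analysis, sample size or power figure changes. This is an optional improvement, not a flaw that threatens a conclusion.

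**What to change.** In SAP Section 13:

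1. Replace a missing Month 6 CD4 count or viral load with the participant's most recent measured on-study result before the Month 6 dose. Use the enrolment value only if there is none, and the stratum median only if there is no result at all.
2. State that a result from the 14 days before visit 5 counts as the Month 6 value.
3. Leave acute COVID-19-visit draws out of the main rule, or use them only in a sensitivity analysis. Do not list new HIV diagnosis as a source.
4. Tabulate how many values come from each source.

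Separately, reconcile SAP 8.2.1 with SAP 11.4.3 on whether exploratory II uses baseline or Month 6 values.

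The cost is a few sentences in the SAP and a line or so of derivation code, using data already collected.

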## Appendix F Laboratory Procedures for the PBMC Immune Correlates subset (Group 1, HIV positive, SARS-CoV-2 seronegative participants)

Procedure	Ship to 	Assay	Location 	Tube 	Tube  capacity 	Vac 1	Vac 2	Vac 3
BLOOD COLLECTION								
Screening/Diagnostic								
HIV test 		01	02	03	04	05	06	07
HIV Viral Load 		D1	D29	D57	D169	D197	D231	D265
CD4+ T Cell Count 		W0	W4	W8	W24	W32	W38	D299
SARS-CoV-2 POC Serology		M0	M1	M2	M6	M7	M8	D396
SARS-CoV-2 Serology		BARC	Local Lab	EDTA	5mL	5	—	W43
Immunogenicity assays		BARC	HVTN Labs	ACD	8.5mL	—	—	W48
Cellular assays 		BARC	HVTN Labs	SST	8.5mL	—	—	W52
Humoral assays		BARC	HVTN Labs	Tempus	3mL	—	—	W61
Visit total					20.0	114.5	0.0	D333
56-Day total					20.0	134.5	134.5	112
NASAL SWAB SAMPLE COLLECTION								
SARS-CoV-2 PCR	Local Lab	Local Lab	—	X	X	X	X	X
SARS-CoV-2 Viral Sequencing 	BARC	HVTN Labs	—	X 	X 	X 	X 	X 
URINE COLLECTION								
Pregnancy Test 	Local Lab	Local Lab	X	—	—	—	—	—

BARC = Bio Analytical Research Corporation South Africa (Pty) Ltd (Johannesburg, South Africa)

HVTN Laboratories include: Bio Analytical Research Corporation South Africa (Pty) Ltd (BARC) (Johannesburg, South Africa); Fred Hutchinson Cancer Center (Seattle, Washington, USA); Duke University Medical Center (Durham, North Carolina, USA); Cape Town Immunology Laboratory (CIL, Cape Town, South Africa); KwaZulu-Natal Research and Innovation Sequencing Platform (KRISP, Durban, South Africa)

Screening may occur over the course of several contacts/visits up to and including Day 1 prior to study product administration.

Local 1 labs may assign appropriate alternative specimen type, tube and volume for locally performed tests.

HIV diagnostic test will be performed for all participants at screening and as clinically indicated.

HIV Viral Load and CD4+ T Cell Count will be performed at screening or at any visit for participants with newly diagnosed HIV infection, at enrollment for known PLWH, approximately 4-6 weeks after any change in antiretroviral therapy (other than just dosage) for PLWH, at visit 5 for PLWH, and as clinically indicated (see Sections 9.2, 9.3, 9.4 and 9.9). HIV Viral Load and CD4+ T Cell Count do not need to be recollected if they were collected and the results available within the past 14 days.

Nasal swab sample will only be sent to site processing lab for processing and storage if local testing results at the same visit return as SARS-CoV-2 infected.

Pregnancy test will be performed at screening for all participants who were assigned female sex at birth and are of reproductive potential. A pregnancy test will be performed at other visits if the participant reports a new pregnancy and / or as clinically indicated.

8x10mL NaHep tubes may be used if ACD tubes are not available

## Appendix G Laboratory Procedures for the PBMC Immune Correlates subset (Group 2, HIV positive, SARS-CoV-2 seropositive participants)

Procedure	Ship to 	Assay	Location 	Tube 	Tube  capacity 	Vac 1	Vac 2
BLOOD COLLECTION							
Screening/Diagnostic							
HIV test 	Local Lab	Local Lab	EDTA	5mL	5	—	—
HIV Viral Load 	Local Lab	Local Lab	EDTA	5mL	5 	—	—
CD4+ T Cell Count 	Local Lab	Local Lab	EDTA	5mL	5 	—	—
SARS-CoV-2 POC Serology	Local Lab	Local Lab	EDTA	5mL	5	—	—
SARS-CoV-2 Serology	BARC	HVTN Labs	SST	5mL	5	—	—
Immunogenicity assays							
Cellular assays 	BARC	HVTN Labs	ACD	8.5mL	—	—	—
Humoral assays	BARC	HVTN Labs	SST	8.5mL	8.5	85	—
Gene Expression	BARC	HVTN Labs	Tempus	3mL	6	6	—
Visit total				20.0	114.5	104.5	0.0
56-Day total				20.0	134.5	239.0	29.5
NASAL SWAB SAMPLE COLLECTION							
SARS-CoV-2 PCR	Local Lab	Local Lab	—	—	X	X	X
SARS-CoV-2 Viral Sequencing 	BARC	HVTN Labs	—	X 	X 	X 	X 
URINE COLLECTION							
Pregnancy Test 	Local Lab	Local Lab	X	—	—	—	—

Greyed out Visit 4 does not apply to this group.

BARC = Bio Analytical Research Corporation South Africa (Pty) Ltd (Johannesburg, South Africa)

HVTN Laboratories include: Bio Analytical Research Corporation South Africa (Pty) Ltd (BARC) (Johannesburg, South Africa); Duke University Medical Center (Durham, North Carolina, USA); KwaZulu-Natal Research and Innovation Sequencing Platform (KRISP, Durban, South Africa)

Screening may occur over the course of several contacts/visits up to and including day 1 prior to study product administration.

Local labs may assign appropriate alternative specimen type, tube and volume for locally performed tests.

HIV diagnostic test will be performed for all participants at screening and as clinically indicated.

HIV Viral Load and CD4+ T Cell Count will be performed at screening or any visit for participants with newly diagnosed HIV infection, at enrollment for known PLWH, at visit 5 for PLWH, and as clinically indicated (see Sections 9.2, 9.3, 9.4 and 9.9). HIV Viral Load and CD4+ T Cell Count do not need to be recollected if they were collected and the results available within the past 14 days.

Nasal swab sample will be only be sent to site processing lab for processing and storage if local testing results at the same visit return as SARS-CoV-2 infected.

Pregnancy test will be performed at screening for all participants who were assigned female sex at birth and are of reproductive potential. A pregnancy test will be performed at other visits if the participant reports a new pregnancy and / or as clinically indicated.

8x10mL NaHep tubes may be used if ACD tubes are not available

## Appendix H Schedule of clinic procedures for Groups 1 and 3 (SARS-CoV-2 seronegative participants)

Visit Number	01	02	03	04	05	106	107	108	109	110	111	112	113	114	115	116	117
Study Week	0	4	8	24	28	33	38	43	48	52	56	61	65	69	74	78	
Study Month	0	1	2	6	7	8	9	10	11	12	13	14	15	16	17	18	
Study Day	-56 to 1	1	29	57	169	197	231	265	299	333	365	396	426	456	486	516	547
Procedure	Screen	Vac 1	Vac 2	Vac Follow up	Vac 3	Follow up											
Study procedures																	
Assessment of Understanding	✓																
Informed consent	✓																
Medical history 	✓																
Physical exam 	✓																✓
Obtain demographics	✓																
Risk assessment questionnaire	✓																
Targeted concomitant medications 	✓	✓	✓	✓	✓	✓	✓	✓	✓	✓	✓	✓	✓	✓	✓	✓	✓
Vaccination 	✓	✓	✓	✓	✓	✓	✓	✓	✓	✓	✓	✓	✓	✓	✓	✓	✓
Ultrasound for gestational age 	✓																
COVID-19 surveillance 	✓																
SAEs, AESIs 	✓	✓	✓	✓	✓	✓	✓	✓	✓	✓	✓	✓	✓	✓	✓	✓	✓
Safety Subset participants 																	
Reactogenicity assessment	✓	✓	✓	✓	✓	✓	✓	✓	✓	✓	✓	✓	✓	✓	✓	✓	✓
AEs for 28 days postvaccination	✓	✓	✓	✓	✓	✓	✓	✓	✓	✓	✓	✓	✓	✓	✓	✓	✓
Specimen Collections																	
Pregnancy test 	✓																
HIV diagnostic test 	✓																
Blood draw 	✓ 	✓	✓	✓	✓	✓	✓	✓	✓	✓	✓	✓	✓	✓	✓	✓	✓
Nasal swab 	✓	✓	✓	✓	✓	✓	✓	✓	✓	✓	✓	✓	✓	✓	✓	✓	✓

 Medical history: Targeted medical history is performed during screening. At enrollment and at subsequent visits, an interim medical history may be performed.

 Abbreviated physical exam will be performed at screening, at the month 12 visit and at the last visit. At other clinic visits a physical exam will be performed as needed, based on participant self-reported symptoms or indications of illness.

 Targeted concomitant medication will be assessed for high-risk conditions.

 Vaccination (in clinic assessments): At least 15 minutes after each vaccination and prior to clinic discharge, the injection site will be assessed, and systemic symptoms will be assessed (see Section 9.3 for detail).

 Ultrasound to evaluate gestational age and for presence of fetal anomalies will be performed for all participants confirmed to be pregnant at enrollment or any other visit, and as clinically indicated, if the participant intends to continue with the pregnancy.

 COVID-19 surveillance: prespecified symptoms that meet the criteria for suspicion of COVID-19 will be elicited approximately every 2 weeks from the participant (see Section 9.5). (Note: All participants who have not exited the study will be contacted as specified, regardless of where they are in the post-enrollment follow-up.)

 Solicited and unsolicited AEs collected for a subset of study participants. Serious adverse events and adverse events of special interest (see Appendix L) collected for all participants throughout the study.

 Pregnancy test will be performed at screening for all participants who were assigned female sex at birth and are of reproductive potential. A pregnancy test will be performed at other visits if the participant reports a new pregnancy and / or as clinically indicated.

 HIV diagnostic test will be performed for all participants at screening and as clinically indicated. Participants with a positive HIV status will be offered HIV counseling. They will also be referred for care and treatment according to local guidelines.

 For details on blood draws see Appendix B, Appendix D and Appendix F.

 Blood sample will be drawn to determine SARS-CoV-2 serostatus (see Section 9.2).

 Two nasal swabs will be collected at each indicated visit.

